### **4. Key Exclusion Criteria**

Subjects who present with and/or self-report the following criteria will not be eligible to participate in the study.

#### Smoking Behavior

1. Current enrollment or plans to enroll in another smoking cessation program in the next 4 months.
2. Regular (daily) use of electronic cigarettes, chewing tobacco, snuff, snus, cigars, cigarillos, or pipes.
3. Current use or plans to use nicotine substitutes (gum, patch, lozenge, e-cigarette) or smoking cessation treatments in the next 4 months.

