**Smoking and Cognition: Deficits Produced during Abstinence and the Relationship to Relapse.** The nicotine withdrawal syndrome is complex as the time course and nature of symptoms vary across smokers (Hughes, 2007b; Shiffman et al., 2006). In addition to the physiological and psychological symptoms of nicotine withdrawal, cognitive impairment is common, reported by nearly 50% of smokers (Hughes, 2007c). These abstinence-induced cognitive impairments peak during the first few days after a quit attempt (Hendricks et al., 2006; Hughes, 2007c; Shiffman et al., 2006) and can be measured objectively in animals and humans. Data across species support the reversal of these effects following administration of nicotine or medications efficacious for smoking cessation (Davis et al., 2005; Patterson et al., 2009; Portugal and Gould, 2007). Interestingly, the domains of cognitive function impaired during abstinence are qualitatively similar to those observed in HANDs (Antinori et al., 2007; McArthur et al., 2010; Robertson and Yosief, 2014; Woods et al., 2004) and include attention (Myers et al., 2005), working memory (Jacobsen et al., 2005; Mendrek et al., 2006), and response inhibition ([name] and Hawk, 2012; Harrison et al., 2009). The clinical relevance of abstinence-induced cognitive deficits is supported by the high prevalence in treatment seeking smokers (Covey et al., 2008; Hughes, 2007b; Rukstalis et

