#### 2. Design

**Main Study.** This study will use a prospective observational matched-design to test whether HIV+ smokers (vs. HIV-smokers) are more likely to experience cognitive deficits during nicotine withdrawal and whether these deficits are predictive of smoking relapse. As shown in Figure 1, adult treatment-seeking smokers (N=300; 150 HIV+ and 150 HIV-) will complete this 12-week study, which is divided into two phases: a pre-quit laboratory phase (weeks 0-2) and a treatment phase (weeks 3-12). Subjects will complete two laboratory sessions during the pre-quit phase: once following 24 hours of mandatory smoking abstinence and once while smoking-as-usual (order counter-balanced; abstinence biochemically confirmed). A cognitive task battery assessing working memory, sustained attention, and response inhibition will be administered during each session. During the treatment phase, subjects will receive standard smoking cessation treatment, including six sessions of brief individual counseling (weeks 3-8) and eight weeks of open-label transdermal nicotine (TN) patch treatment (weeks 4-12) [34]. The primary outcomes will be: 1) cognitive performance (e.g., verbal and working memory) following 24-hours smoking abstinence (vs. smoking-as-usual) during the pre-quit phase, and 2) 7-day point-prevalence, biochemically confirmed abstinence rates at end-of-treatment (EOT) for the treatment phase. Since randomization is not possible in this study, we will rely on inclusion criteria and matching to reduce the potential for confounding. More specifically, participants will be

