10. **HIV-negative only:** Complete an on-site HIV test with a nurse trained to administer HIV testing and to do required reporting and counseling should a participant test positive for HIV.
11. Provide one 10ml blood sample (2 teaspoons) to assess nicotine metabolite ratio (cotinine and 3-hydroxycotinine).
12. Provide one 8ml blood sample (2 teaspoons) for examining biomarkers of neuroinflammation.

**HIV-positive** participants will be asked to provide lab work to confirm recent viral load of less than or equal to 1000 copies/mL and CD4+ counts of greater than or equal to 200 cells/mm^3 within 12 months prior to enrollment. If a participant is unable to provide lab work, their clinic may be contacted to obtain the necessary documentation.

If eligible at this point, subjects will schedule their first laboratory session (Week 1).

**Laboratory Session 1 (Week 1).** This visit should occur within eight weeks of Intake. Allowances may be made for staff or subject scheduling conflicts. This in-person visit is expected to last 1-1.5 hours. During this visit, participants will:

1. Provide urine specimens for drug and (if applicable) pregnancy tests (See Exclusion Criteria above and Measures below).
2. Provide a CO sample.
  - a. During the smoking session: To standardize smoking across participants, they will smoke a cigarette about 30-40 minutes prior to beginning the cognitive task battery, as in our past studies ([name] and Hawk, 2012; [name] et al., 2014; [name] et al., 2013a; Tsaur et al., 2015)
  - b. During the abstinent session: Participants must have CO readings less than 10ppm or less than 50% CO reading taken at Intake in order to be eligible for the study.
3. Complete questionnaires (see Table 1. Study Measures). Measures may be completed remotely via RedCap to reduce the length of in-person tasks.
4. MADRS, YMRS, Bipolar Disorder Additional Screener, if necessary. Screening measures may be completed remotely via RedCap to reduce the length of in-person tasks.
5. Complete a 1-hour battery of computer tasks which may include tasks assessing working memory (n-back), executive function (Stroop task), response inhibition (stop-signal task), and delay discounting.

**Laboratory Session 2 (Week 2).** Participants will complete the same activities they completed at Laboratory Session 1 in the alternate smoking condition. The following activities may also take place:

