#### **Screening/Covariate Measures.**

**Demographics and Smoking History.** Standard questionnaires will be administered remotely or in-person at the Intake visit to collect the following data: demographics (age, gender, marital status, education), age at smoking initiation, cigarette brand, length of prior abstinence periods and current smoking rate. The Fagerstrom Test for Nicotine Dependence (FTND) will also be administered. The FTND is a 6-item, self-report measure of nicotine dependence derived from the Fagerstrom Tolerance Questionnaire (Heatherton et al., 1991). The FTND scale has satisfactory internal consistency (Cronbach's alpha=.64) and high test-retest reliability (r=.88) (Pomerleau et al., 1994).

**Urine Drug Screen.** The urine drug screen will be administered at Intake, Lab session 1 and Lab session 2. The urine drug screen requires about 30ml of urine and indicates whether the subject has recently taken any of the following: cocaine, PCP, amphetamines, methamphetamines, tricyclic antidepressants, ecstasy, opiates, methadone, benzodiazepines, THC, and barbiturates. Participants with a positive urine drug screen for cocaine, methamphetamines, PCP, barbiturates, ecstasy (MDMA) may be deemed ineligible. The rationale for excluding these participants is because one of the primary outcomes in this study is cognitive function. Thus, excluding individuals who screen positive for substances that may interfere with their ability to perform the cognitive tasks (e.g., barbiturates may slow reaction times) reduces this potential source of variability. In an effort to remain CLIA-compliant, results from urine drug screening will not be shared with participants. Participants will be informed that the testing is for research purposes only and that they will be informed of their eligibility status, but not of the specific testing results.

**Urine Pregnancy Test.** At the Intake, Lab 1 and Lab 2 sessions, participants will be supplied with a simple, CLIA-waived urine pregnancy screen and informed that pregnant women are not advised to participate in this research study.

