#### Nicotine Metabolic Rate (3-HC/cotinine ratio/TNE).

One baseline blood sample will be collected at Intake and analyzed for nicotine metabolites to determine rate of nicotine metabolism. Nicotine is metabolized to cotinine and then to 3-HC by the P450 (CYP) 2A6 enzyme (Nakajima et al., 1996). The 3-HC/cotinine ratio is a stable measure of the rate of nicotine metabolism, which influences response to nicotine dependence treatments (Lerman et al., 2006; Patterson, Schnoll et al., 2008). Evidence also suggests that HIV-infected smokers metabolize nicotine faster than HIV-uninfected smokers (Earla et al., 2014). Therefore, the NMR will be evaluated as a potential moderator of abstinence-induced cognitive deficits and as a covariate in relapse analyses. Urinary concentrations of NIC and its nine metabolites will be analyzed using liquid chromatography tandem mass spectrometry, as described previously (T. Taghavi et al., submitted manuscript). Urine samples will be diluted and prepared using solid-phase extraction adapted from a previously established method (Miller et al., 2010). The limit of quantification was 1 ng/ml for all compounds. The primary outcome is Total nicotine equivalents (TNE), in nanomole per milligram creatinine, will be calculated as the molar sum of NIC and all nine metabolites (COT, 3HC, NIC-GLUC, COT-GLUC, 3HC-GLUC, NNO, CNO, NNIC, and NCOT) and will be corrected using scaled creatinine data. Urinary creatinine concentrations will be determined using a colorimetric assay according to protocol provided in the Creatinine Assay Kit (MAK080) purchased from Sigma-Aldrich (St. Louis, MO) with a SynergyMX Analyzer (BioTek, Winooski, VT). The

biosamples of individuals who complete the Pre-Quit visit will be sent to the laboratory of [name] at the University of Toronto for analysis. These analyses will be exploratory.

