#### **Other Smoking Measures (secondary).**

The total number of days abstinent during the first 7 days following the TQD, confirmed with CO, will be a secondary outcome measure. We have shown that this measure is highly predictive of long-term abstinence ([name] et al., 2013b). Other secondary smoking outcomes include: prolonged abstinence to EOT (week 12) where relapse is 7 consecutive days of self-reported smoking, after a 2-week grace period; continuous abstinence at EOT (no smoking between the TQD and the follow-up; time to 7-day relapse (no grace period); and lapse (smoking episodes not lasting 7 days) and recovery (return to 24-hour abstinence) events (see (Schnoll et al., 2010)).

**Cessation/Smoking Rate:** Daily smoking (presence and rate) will be assessed at each visit after the Intake Session with the well validated timeline follow-back method (TLFB). These data can be used to assess the timing and rates of lapses (smoking episodes not lasting 7 days), recovery events (return to abstinence), and relapse events, as well as to monitor changes in smoking rates (i.e., # cigarettes/day). These data will also be used to compute and assess secondary measures of smoking cessation (e.g., continuous and prolonged abstinence).

**Carbon Monoxide (CO) Test:** Carbon monoxide will be measured by staff at Intake and the Lab sessions. Following Lab session 2, subjects will be asked to self-report their CO levels using an iCO device (carbon monoxide reader) that will be provided to them at Lab session 2. The iCO smokerlyzer (CoVita, Santa Barbara, CA) is a personal breath smokerlyzer monitor for use with a smartphone or tablet. It works in conjunction with the Smokerlyzer app on iOS and android phones or tablets. The iCO device provides biofeedback from a simple breath test, and it also allows users to track their progress. The app also provides an exhalation guide to coach users on the proper technique to ensure accurate results. The device can be connected to the users' phone through the headphone jack or via Bluetooth. Participants with iOS devices who require adapters will be provided with them by staff. Participants who do not have a smartphone or tablet, or are unable to use the device, will be asked to report to our center for a carbon monoxide assessment if they report abstinence. Since the iCO device cannot be sanitized and does not come with changeable mouthpieces, participants will be advised to limit use of the device to only themselves.

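### The abstinent lab session is defined by smoking and verified by breath CO, so eligible non-daily smokeless tobacco users can be tested with nicotine on board and still count as abstinent

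*Combined protocol and SAP*

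**What the plan says.** **Eligibility.** Under Key Exclusion Criteria, Smoking Behavior, item 2 excludes "Regular (daily) use of electronic cigarettes, chewing tobacco, snuff, snus, cigars, cigarillos, or pipes". Item 3 excludes "Current use or plans to use nicotine substitutes (gum, patch, lozenge, e-cigarette) or smoking cessation treatments in the next 4 months". Item 2 has a frequency threshold and item 3 has none. E-cigarettes appear in both. Chewing tobacco, snuff and snus appear only in item 2.

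**The manipulation.** The Design section has each participant tested twice, "once following 24 hours of mandatory smoking abstinence and once while smoking-as-usual". For the abstinent session, Laboratory Session 1 (Week 1) gives the check: "Participants must have CO readings less than 10ppm or less than 50% CO reading taken at Intake". Laboratory Session 2 repeats the same activities in the other condition. Self-report is a timeline follow-back of smoking: "Daily smoking (presence and rate) will be assessed at each visit after the Intake Session".

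**Nicotine measurement.** Metabolites are measured at entry: "One baseline blood sample will be collected at Intake and analyzed for nicotine metabolites". Table 1 marks the urine and plasma metabolite measure at Intake only. The urine screen at Intake and both lab visits covers "cocaine, PCP, amphetamines, methamphetamines, tricyclic antidepressants, ecstasy, opiates, methadone, benzodiazepines, THC, and barbiturates"; neither nicotine nor cotinine is in the panel.

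**The premise.** The Background paragraph on smoking and cognition says of abstinence-induced impairments: "Data across species support the reversal of these effects following administration of nicotine or medications efficacious for smoking cessation".

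**The concern.** The construct under study is cognitive deficit during nicotine withdrawal, but the session rule covers smoking only. A participant who uses snus, snuff or chewing tobacco occasionally can enrol, use it during the 24 hours, pass the CO check and be analysed as abstinent without breaking a stated rule. On the protocol's own premise, that session may show little or no deficit.

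The change between sessions is the Aim 1 outcome, and the same task differences are the candidate mediators in Aim 3. Sessions without withdrawal therefore enter both analyses. HIV status is not randomized, and the four matching factors (age, race, education, smoking rate) do not include other nicotine products, so nothing in the design makes such use equal between groups.

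The protocol does control comparable threats. It screens for drugs that could affect task performance at both lab visits, tests as-needed opiate users who were told to refrain, and times a cigarette before testing in the smoking session. It has no matching control on nicotine in the abstinent session.

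**Working it through.** **1. Which products can reach the abstinent session**

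| Product, non-daily use | Item 2 | Item 3 | Study-NRT-only instruction (Medication Exclusion Criteria, item 1 note) | Shown by CO? |
|---|---|---|---|---|
| E-cigarette | not caught | excluded | not named | no |
| Gum, patch, lozenge | not listed | excluded | covered | no |
| Chewing tobacco, snuff, snus | not caught | not listed | not named | no |
| Cigars, cigarillos, pipes | not caught | not listed | not named | yes, burned |

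The open route is non-daily smokeless tobacco. E-cigarettes join it only if screeners apply item 2 in place of item 3.

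**2. What at the lab visit would reveal it**

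CO does not register products that are not burned, whatever the cutoff. The follow-back concerns smoking. The urine panel has no cotinine, and metabolites are taken only at Intake. The Concomitant Medication Review, which Table 1 marks at both lab visits, asks about medications and substances. It might pick up such use, but it is framed around response to study medication and has no stated consequence for whether a session counts.

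**3. The plan's own power figure**

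Inputs from Power Analysis and Sample Size: 150 per group, alpha 0.05/5 = 0.01, d = 0.4, power 80%. Assumed here: a two-sided test, with d as the between-group difference in change scores in SD units.

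Normal approximation: power = Φ(d√(n/2) − 2.576). With √75 = 8.660, 0.4 × 8.660 = 3.464, and Φ(0.888) = 81.3%. The noncentral t gives 80.8%. The stated 80% reproduces; 146 per group would be needed for it.

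**4. Equal use in both groups**

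Assume that a fraction f of abstinent sessions in each group shows no deficit and that the SD is unchanged. Then d = 0.4(1 − f).

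| f (assumed) | d | Power, t | Power, normal | N per group for 80% |
|---|---|---|---|---|
| 0 | 0.400 | 80.8% | 81.3% | 146 |
| 2% | 0.392 | 78.8% | 79.4% | 153 |
| 5% | 0.380 | 75.7% | 76.3% | 162 |
| 10% | 0.360 | 70.0% | 70.6% | 181 |
| 20% | 0.320 | 57.1% | 57.7% | 229 |

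**5. Unequal use**

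Let m be the HIV− deficit and m + 0.4 the HIV+ deficit. The observed difference is (m + 0.4)(1 − f₊) − m(1 − f₋). With m = 0.2 assumed (normal approximation):

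- 10% in HIV+ only: 0.6 × 0.9 − 0.2 = 0.34, power 64.4%.
- 10% in HIV− only: 0.6 − 0.2 × 0.9 = 0.42, power 85.6%.

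With no true interaction, an assumed common deficit of 0.5 SD and use of 15% against 5%, the false difference is (0.15 − 0.05) × 0.5 = 0.05 SD. Its noncentrality is 0.05 × 8.660 = 0.43, which raises the two-sided false-positive rate from 1.0% to about 1.7%.

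**The case against.** **The exclusions are stricter than they look.** A reader might infer that items 2 and 3 contradict each other on e-cigarettes, or that an occasional vaper could enrol and comply with every rule. The documents do not support either reading. The Key Exclusion Criteria apply jointly, so meeting any one makes a person ineligible, and item 3 already removes any current e-cigarette user. The items overlap, with item 2's e-cigarette entry redundant. They may also be meant to separate product use from use as a substitute. This objection stands. What remains is one product under two frequency thresholds, which screeners could apply differently.

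**NRT is covered.** Eligible participants are told to use only study-supplied NRT, and patch use starts at the target quit day, after both lab sessions. This stands for NRT, but the instruction does not name smokeless tobacco.

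**Other measures might show it.** Besides the concomitant review, the withdrawal and craving scales are given at both lab sessions with a 24-hour reference. They could suggest that a session produced no withdrawal. Neither is prespecified as a check on the manipulation, and low scores would not identify nicotine use.

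**The instruction may be elsewhere.** The inclusion criteria refer to restrictions in the consent form, which is not available here, and a Manual of Operations is to be written. Either may tell participants to avoid all nicotine, so it cannot be said that no such instruction exists. That would not change the validity rule the protocol states, which rests on smoking and CO.

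**The affected share may be tiny.** It is the share of non-daily smokeless users multiplied by the share of them who use in one particular 24-hour window. This is fair, and it limits what can be claimed about size.

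**Conclusion.** The point holds for non-combusted nicotine, mainly non-daily smokeless tobacco. The stated rule would accept as abstinent a session in which the participant is not in withdrawal, and no lab-visit measure is designed to find it.

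The size cannot be set from the documents, which give no rate of use. At 2% of sessions the loss is about two points of Aim 1 power (80.8% to 78.8%); at 10% it is about eleven (to 70.0%). These figures also assume that the deficit is wholly abolished in affected sessions. A reader might infer from the 20% row that a severe loss of power is expected, but nothing in the documents supports a rate that high. Nor does contamination always shrink the interaction: if use differs by HIV group it can move the estimate either way, and the false-positive illustration is small. The Aim 3 mediators are exposed through the same change scores; no figure is given for them.

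This is an improvement worth making because it is cheap, not a flaw shown to invalidate either aim.

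**What to change.** 1. In the Design section and in Laboratory Sessions 1 and 2, define the abstinent session as 24 hours without any tobacco or nicotine product. Keep the CO check for smoking.
2. At both lab visits, ask about use of all such products in the past 24 hours and record the answer.
3. Treat an abstinent session with reported use as not abstinent and reschedule it. At minimum, exclude such sessions in a prespecified sensitivity analysis for Aims 1 and 3.
4. Reconcile exclusion items 2 and 3 so that e-cigarettes fall under one stated rule.

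The cost is protocol wording, one added question at two existing visits and a few rescheduled sessions, with no new assay. The limit is that detection would rest on self-report, so unreported use would remain.

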#### Alcohol/Drug Exclusion Criteria

1. Current untreated and unstable diagnosis of substance dependence (eligible if past use and if receiving treatment and stable for at least 30 days). Current untreated and unstable diagnosis of substance abuse requires Study Physician approval.
2. A positive urine drug screen for cocaine, methamphetamines, PCP, barbiturates, ecstasy (MDMA) at Intake (see Measures and Table 1 for details). At Lab 1 and Lab 2, positive urine drug screens will be reviewed on a case-by-case basis. The PI will determine if the participant will be excluded or allowed to reschedule the visit, at which time they must provide a negative drug screen to continue with the study. Participants believed to have a false-positive result on the drug screen may continue in the study, with investigator approval.

#### Medication Exclusion Criteria

Current use or recent discontinuation (within last 14 days) of the following medications:

1. Other smoking cessation medications (e.g. Zyban, Wellbutrin, Wellbutrin SR, Chantix)
  - a. Note: Once participants are found eligible for the study, they are instructed to only use the NRT provided to them by the study staff. If a subject reports using a non-study smoking cessation medication (including

other forms of NRT), the study physician and PI will evaluate the situation and determine if it is safe for the subject to continue participation.

2. Anti-psychotic medications (if used to treat psychotic symptoms. Other uses may be eligible pending physician approval).
3. Daily use of opiate-containing medications for chronic pain (Duragesic/fentanyl patches, Percocet, Oxycontin). Smokers who report taking opiate-containing medications on an “as-needed” basis will be instructed to refrain from use until their study participation is over and that they will be tested to ensure they have complied with this requirement.
4. Asthma medications/corticosteroids (require physician approval)
5. Anti-depressants (require physician approval)

